- 5. Significant hearing or visual impairment that may affect the participant's ability to complete the test procedures.
- 6. Concurrent major psychiatric condition (e.g., Major Depressive Disorder, Schizophrenia or Bipolar Disorder) as diagnosed by the investigator. Participants with additional diagnosis of Autism Spectrum Disorder or Anxiety Disorder will be allowed as these are characteristics of FXS.

- 7. Participant has active diseases that would interfere with participation, such as acquired immunodeficiency disorder, hepatitis C, hepatitis B, or tuberculosis.
- 8. Participant is planning to commence psychotherapy or cognitive behavior therapy (CBT) during the period of the study or had begun psychotherapy or CBT within 4 weeks prior to Screening.
- 9. Participant has participated in another clinical trial within the 30 days preceding Screening.

Investigational Product, Dosage, and Mode of Administration:

In this single-blind, 4-period study, 15 participants will be enrolled and will be treated with the following during the 4 periods of the study.

- Ergoloid mesylates 1 mg TID (Medisca)* and matching placebo for 5-Hydroxytrptophan 100mg TID***
- Ergoloid mesylates 1 mg TID (Medisca) and 5-Hydroxytryptophan 100 mg TID (5-HTP, Basic Vitamins)**
- 5-Hydroxytryptophan 100 mg TID (5-HTP, Basic Vitamins) and matching placebo for Ergoloid mesylates 1mg TID***
- Matching placebo for Ergoloid mesylates 1mg TID and Matching placebo for 5-Hydroxytryptophan 100mg TID***
- •

* 1 mg will be mixed with methyl cellulose and placed in a size 00 capsule

** will be over-encapsulated in identical size 00 capsules

***will be ascorbic acid powder in identical size 00 capsules

All study medications will be prepared at the Rush Oak Park Compounding Pharmacy and provided to the RUMC Investigational Pharmacy for dispensing as identical-appearing capsules in bottles. Two bottles of capsules will be provided at each visit and one capsule from each bottle will be taken 3 times a day. Doses should be taken at least 4 hours apart.

Overview of Endpoints

Exploratory Efficacy Outcome Measures

- NIH-TCB: Cognitive battery assessing different domains of cognition, administered using an iPad
- KiTAP: Computerized executive battery with assessments of alertness (reaction time), distractibility, go/nogo (impulsiveness), and flexibility
- Clinical Global Impression Severity Investigator rated (CGI-S) Standardized ranking scale with 7 rankings
- Clinical Global Impression Improvement Investigator rated (CGI-I): Standardized ranking scale with 7 rankings
- Visual Analog Scale (VAS) Parent/caregiver-rated assessment of participant-specific behavioral anchors: Domains of daily functioning, anxiety/irritability and language.
- ABC: Parent/caregiver-rated scale with six subscales to assess irritability, social avoidance, lethargy, hyperactivity, inappropriate speech and social avoidance, using ABC-FX factoring system.
- ADAMS: Parent/caregiver rated scale with a total score and five sub-scores to assess manic/hyperactive behavior, depressed mood, social avoidance, general anxiety, and obsessive/compulsive behavior.
- Vineland-3 Adaptive Behavior Scale: Clinician-administered standardized interview yielding adaptive behavior composite score and domain standard scores in domains of: communication (receptive, expressive, and written adaptive language functions), daily living skills (personal, domestic, and community skills), socialization (interpersonal relationships, play and leisure time, and coping abilities), and motor skills (gross and fine motor skills).
- Event-Related Potentials (ERP) Measure of auditory habituation based on EEG signals
- Eye Tracking Measure of gaze aversion (social anxiety) and pupilometry (autonomic function)

Safety and Tolerability: The safety variables to be assessed include adverse events; clinical laboratory parameters (chemistry, hematology, and urinalysis); physical examinations; and vital signs (including blood pressure, heart rate, and respiratory rate).

Statistical Considerations

Efficacy Analyses

The primary efficacy population will be the intent to treat (ITT) efficacy population, which will include all participants who received at least one dose of treatment and returned for at least one follow-up visit. The completers population (CP), defined as all randomized participants who complete all 4 treatment periods with no significant protocol violations, will be used to evaluate the robustness of the ITT results.

All efficacy parameters will be summarized at each time point collected and standard descriptive statistics provided. Baseline measurements are defined as those obtained on Day 1/Period 1 prior to receipt of any study medication. For cognitive parameters measured at baseline, change from baseline will also be calculated and standard descriptive statistics provided for each time point.

Safety Analyses

The Safety population will include all participants who received at least one dose of study treatment. Adverse Events (AEs), including clinically meaningful laboratory abnormalities and significant behavioral changes will be tabulated. AE severity and relatedness to treatment will be assessed. AEs will be tabulated for placebo, EM, EM + 5-HTP and 5-HTP treatments. Summaries will also be provided by severity and relationship to treatment. Serious Adverse Events (SAEs) will be summarized separately, in a manner similar to that used for Adverse Events.

1	TA	BLE OF CONTENTS	
1	TAI	BLE OF CONTENTS	7
2	LIS	T OF ABBREVIATIONS	9
3	intro	oduction	11
	3.1	Background	11
	3.2	Rationale	12
	3.3	Risk/Benefit	12
	3.3	1 Preclinical Pharmacology	12
	3.3	2 Clinical Experience	14
	3.4	Study objectives and endpoints	15
	3.4	1 Study Objectives	15
	3.4	2 Exploratory Efficacy Outcome Measures	15
	3.4	3 Safety and Tolerability Endpoints	16
4	inv	estigational plan	16
	4.1	Overall Study Design	16
	4.1.	1 Dose Selection	16
-	4.2	Study Duration	17
5	sele	ection and Withdrawal of participants	17
	5.1	Study Population	17
	5.2	Participant Inclusion Criteria	I /
	5.5 5.4	Participant Exclusion Criteria	18
	5.4 5.5	Participant withdrawal	19
6	J.J	tmont of participants	19
0	6 1	Treatment Arms	19
	6.2	Study Medications	20
	6.3	Drug Accountability	20
	6.5	Blinding	20
	6.5	Study Drug Administration	20
	6.6	Prior and Concomitant Medications	20
	67	Other Therapeutic Treatments	21
	6.8	Dietary Guidelines	21
	6.9	Lifestyle Guidelines	21
7	stuc	ly procedures and assessments	21
	7.1	Informed Consent	21
	7.2	Medical /Surgical History	21
	7.3	Demographics and Social History	22
	7.4	Stanford Binet Intelligence Scale	22
	7.5	Physical Examination (Full and Abbreviated)	22
	7.6	Height, Weight, Body Mass Index	22
	7.7	Vital Signs	23
	7.8	Laboratory Assessments	23
	7.9	Management of Abnormal Clinical Laboratory Tests	23
	7.10	Additional Safety Measures	23
	7.11	Exploratory Efficacy Assessments	24

	Protocol: ERG/5-HTP in FXS
Date: 23 May 2022 v4.0	Date: 23 May 2022 v4.0

7.11.1 Descriptions of Efficacy Assessment Instruments	24					
7.11.1.1 NIH-TCB	24					
7.11.1.2 Test of Attentional Performance (KiTAP)	24					
7.11.1.3 Clinical Global Impression	25					
7.11.1.3.1 Clinical Global Impression Severity: Investigator Rated (CGI-S)	25					
7.11.1.3.2 Clinical Global Impression Improvement: Investigator –Rated (CGI-I)	25					
7.11.1.4 VAS Rating Scale	25					

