6.4 Blinding

This is a single-blind study, meaning the participant and his family/caregivers will not know what drug or combination the participant is receiving. The investigator and study coordinator will know what drug the participant is taking. The remainder of the study team performing assessments such as the Vineland, eye tracking, ERP, Toolbox, and the KiTAP will not know the type of treatment the patient is on when testing is done.

The PI or designee will be responsible for maintaining the single blind, consistent with protocol design, throughout the study, except in the case of an emergency need to unblind the participant for medical reasons. Blinding is not to be broken during the study unless considered necessary by the Investigator for emergency situations for reasons of participant safety. When the blind is broken, the reason must be fully documented.

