8.3 Assessment of Adverse Events by the Investigator

8.3.1 Causality/Relatedness

The relationship of an adverse event to the administration of the study drug is to be assessed by the Investigator according to the following definitions:

Not Related (unlikely related, unrelated, not related, no relation) – The time course between the administration of study drug and the occurrence or worsening of the adverse event rules out a causal relationship and/or another cause (e.g., medical history, concomitant drugs, therapies, and complications) is suspected.

Related (possibly related, related) – The time course between the administration of study drug and the occurrence or worsening of the adverse event is consistent with a causal relationship and no other cause (e.g., medical history, concomitant drugs, therapies, and complications) can be identified.

The definition implies a reasonable possibility of a causal relationship between the event and the study drug. This means that there are facts (evidence) or arguments to suggest a causal relationship.

The following factors should also be considered:

- The temporal sequence from study drug administration The event should occur after the study drug is given. The length of time from study drug exposure to event should be evaluated in the clinical context of the event.
- Underlying, concomitant diseases (medical history) Each report should be evaluated in the context of the natural history and course of the disease being treated and any other disease the participant may have.
- Concomitant drug The other drugs the participant is taking or the treatment the participant receives should be examined to determine whether any of them might be recognized to cause the event in question.
- Known response pattern for this class of study drug Clinical and/or preclinical data may indicate whether a particular response is likely to be a class effect.
- Exposure to physical and/or mental stresses The exposure to stress might induce adverse changes in the recipient and provide a logical and better explanation for the event.
- The pharmacology and PK of the study drug The known pharmacologic properties (absorption, distribution, metabolism, and excretion) of the study drug should be considered.

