8.3.2 Severity

The Investigator is responsible for assessing the severity (intensity) of each adverse event as mild, moderate, or severe according to the following definitions:

Mild – An event that is easily tolerated and generally not interfering with normal daily activities. Moderate – An event that is sufficiently discomforting to interfere with normal daily activities. Severe – An event that is incapacitating with inability to work or perform normal daily activities. It should be noted that a severe AE need not be serious and that a serious adverse event (SAE) need not, by definition, be severe.

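### An investigator who knows the regimen judges relatedness and severity of adverse events, so the placebo period's related-event count is not a usable comparator

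*Combined protocol and SAP*

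**What the plan says.** The Safety Analyses paragraph of the synopsis sets out AE columns for placebo, EM, EM + 5-HTP and 5-HTP, and continues: "Summaries will also be provided by severity and relationship to treatment". Section 10.5 repeats that sentence but names the columns as placebo and BPN14770, a product that is not in this study.

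On blinding, 6.4 says: "The investigator and study coordinator will know what drug the participant is taking". Participants and caregivers are blinded, and so are the testers: "The remainder of the study team performing assessments such as the Vineland, eye tracking, ERP, Toolbox, and the KiTAP will not know" the treatment when they test. AE assessment is not in that list.

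On who judges, 8.3.1 says: "The relationship of an adverse event to the administration of the study drug is to be assessed by the Investigator". Section 8.3.2 says: "The Investigator is responsible for assessing the severity (intensity) of each adverse event as mild, moderate, or severe". No blinded or independent AE assessor, adjudication step or interpretive caveat appears anywhere.

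Under 8.3.1 an event is Related when its time course "is consistent with a causal relationship and no other cause" can be found. The factors to weigh include the response pattern of the drug class and "The pharmacology and PK of the study drug".

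Every participant receives placebo last, in Period 4, directly after 5-HTP alone. Section 4.1 states that there is no washout.

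**The concern.** Safety and tolerability is one of the three objectives (3.4.1), and the placebo period is the only comparator in the AE table. On the natural reading, the severity and relationship summaries follow the same regimen columns as that table.

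Two of the relatedness factors in 8.3.1 draw on the identity of the product. An investigator who knows that the capsules hold placebo will seldom find those factors met by the current treatment. The same event in Periods 1 to 3 can readily be called possibly related, which 8.3.1 counts as Related. An excess of related AEs over placebo could therefore appear with no drug effect behind it. Severity grades pass through the same unblinded person, and expectation could move them in either direction.

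**Working it through.** **No plan figure to reproduce.** The documents give no AE rate, no attribution rate and no sample-size calculation (10.1). What follows is an illustration on stated assumptions.

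**Inputs**
- n = 15 participants, each planned to receive all four regimens (synopsis; 4.1).
- p = share of participants with an AE in a period, the same in every period, so there is no true difference. Assumed 40%, with 20% and 60% as the range.
- qA = chance that an event on active drug is called related. Assumed 50%.
- qP = chance that an event on known placebo is called related. Assumed 50%, 25%, 10% or 0%. This is the deciding assumption.

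**Formulas.** Expected related count on active = n × p × qA. On placebo = n × p × qP. False gap = p × (qA − qP).

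**At p = 40%:** the active count is 15 × 0.40 × 0.50 = 3.0.

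| qP | Placebo count | False gap | Chance that placebo shows fewer related cases than one active regimen |
|---|---|---|---|
| 50% | 3.0 | 0 points | 0.41 |
| 25% | 15 × 0.40 × 0.25 = 1.5 | 0.40 × 0.25 = 10 points | 0.70 |
| 10% | 15 × 0.40 × 0.10 = 0.6 | 0.40 × 0.40 = 16 points | 0.87 |
| 0% | 0 | 0.40 × 0.50 = 20 points | 0.96 |

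The last column uses exact binomial counts with the two regimens treated as independent. The same participants supply both columns, so it is only a guide.

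**Range over incidence.** For qP = 25%, 10% and 0%, the gap is 5, 8 and 10 points at p = 20%, and 15, 24 and 30 points at p = 60%.

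**The opposing force.** Suppose a share c of Period 4 events is attributed to the preceding 5-HTP at the active rate of 50%, and the rest are judged at 10%. Let Period 4 have r times as many events as an active period. The ratio of related events, placebo to active, is r × [0.5c + 0.1(1 − c)] / 0.5.

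- r = 1, c = 0: 0.10 / 0.5 = 0.20
- r = 1, c = 0.5: 0.30 / 0.5 = 0.60
- r = 1, c = 0.75: 0.40 / 0.5 = 0.80
- r = 1.5, c = 0.75: 1.5 × 0.40 / 0.5 = 1.20

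Knowledge of the regimen alone lowers the placebo count. Attribution to prior drug raises it and can reverse the gap. The documents fix neither quantity, and no rule says which regimen an early Period 4 event belongs to.

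**The case against.** **A stronger reading is tempting.** A reader might infer that the placebo column must show almost no related events by design, and that a 20-point false difference follows. The documents do not support that. Section 8.3.1 rests on time course and the absence of another cause, and no rule sends placebo-period events to Not Related. With 5-HTP immediately before and no washout, an early Period 4 event may be called related to the earlier drug and still be counted under placebo. The 20 points also require placebo attribution of exactly 0%.

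**The defence of the plan has further points.**
- The study is openly single-blind, exploratory and descriptive. No AE test is planned, so no error rate is affected. This stands, but descriptive tables are the study's only AE output, so their labels matter.
- The safety endpoint is treatment-emergent AEs without regard to cause (3.4.3), and the synopsis table by regimen carries no relatedness filter. This also stands. The table best suited to the comparison is already planned, but the plan does not say that it is the one to use.
- Events are reported largely by blinded participants and caregivers, and 8.3.2 grades severity by interference with daily activities. This limits the exposure of total counts and of severity. It does not remove it for severity, because the unblinded investigator still assigns the grade.
- The synopsis does not say outright that the severity and relationship summaries are by regimen, and 10.5 speaks of frequency and severity over everyone dosed. The by-regimen reading is therefore an inference, though a natural one. If the summaries are pooled, the plan should say so.

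**Conclusion.** The concern holds in a limited form. An investigator who knows the regimen assigns relatedness and severity, and nothing in the plan protects or qualifies the resulting split. The related count on placebo is likely too low by an unknown amount, with a possible opposing push from attribution to prior 5-HTP. It should not be used as a comparator. Severity is open to expectation to a lesser degree, and neither its direction nor its size can be given.

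With no true difference, 40% incidence and 50% attribution on active drug, the false gap is about 10, 16 or 20 points for placebo attribution of 25%, 10% or 0%. All of these rates are assumptions. The point concerns how descriptive tables are read; no test or power statement is affected.

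**What to change.** In the synopsis (Safety Analyses) and 10.5:

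1. State that regimens are compared on all-causality treatment-emergent AEs.
2. Label the relationship and severity summaries as unblinded investigator judgements, and do not contrast relationship with placebo.
3. List Period 4 events judged related separately, noting whether each was attributed to prior 5-HTP, so that they are not lost.
4. Reconcile the AE columns in 10.5, which name BPN14770, with the four regimens in the synopsis.

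The cost is wording, and 10.5 needs revision anyway. The small downside is that the related-AE table no longer offers a placebo contrast. Investigator causality, seriousness and safety decisions are unchanged.

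Having the blinded Vineland rater grade severity is not recommended. The order is the same for everyone, so visit number reveals the regimen to anyone who knows the design. The Vineland visits (14.1) miss events first reported at the Week 17 call, and laboratory AEs have no caregiver account to grade. Taking AE histories could also compromise the blind of someone scoring an efficacy measure.

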2 LIST OF ABBREVIATIONS

ABC (-FX)	Aberrant Behavior Checklist (Fragile X specific factoring system)
ADAMS	Anxiety, Depression, and Mood Scale
AE(s)	Adverse event(s)
ADR	Adverse drug reaction
ALT	Alanine transaminase
bid	Twice daily
BMI	Body mass index
BP	Blood pressure
BPM	Beats per minute
BUN	Blood urea nitrogen
°C	Degrees centigrade
CBT	Cognitive Behavioral Therapy
CFR	Code of Federal Regulations
CGI-I	Clinical Global Impression Improvement – Investigator rated
CGG	CGG trinucleotide repeating codon
CGI-S	Clinical Global Impression Severity – Investigator rated
CNS	Central nervous system
СР	Completers population
CRF	Case report form
DCCS	Dimensional change card sort (test)
EDTA	Ethylenediaminetetraacetic acid
EEG	Electroencephalogram
ERP	Event-Related Potentials
FDA	Food and Drug Administration
FMR1	Fragile X mental retardation
FXS	Fragile X Syndrome

gm	Gram
GCP	Good Clinical Practice
GI	gastrointestinal
HgbA1C	Hemoglobin A1C
ICF	Informed consent form
ICH	International Conference on Harmonization
IRB	Institutional Review Board
ITI	Inter-trial interval
ITT	Intent to treat (population)
kg	kilogram
KiTAP	Test of Attentional Performance
mg	Milligram
mL	Milliliter
msec	Millisecond
μ	Micro
ng	Nanogram
NIH-TCB	NIH Toolbox Cognitive Battery for Intellectual Disabilities
РО	By mouth (per os)
RBC	Red blood cell
ROI	Region of interest
SAE	Serious adverse event
SD	Standard deviation
SOP	Standard operating procedure
VAS	Visual analog scale

3 INTRODUCTION

3.1 Background

Mutational inactivation of the *FMR1* gene encoding the Fragile X Mental Retardation protein (FMRP) causes a spectrum of symptoms including seizures, sleep disorders, anxiety, irritability, autism, mild to severe cognitive impairment and intellectual disability. The constellation of symptoms is known as Fragile-X syndrome (FXS).

FXS in humans is caused by a CGG triplet expansion mutation (> 200 repeats) in the 5' untranslated region of the *FMR1* gene located on the X chromosome, which leads to gene methylation, inactivation, and resultant loss of fragile X mental retardation protein (FMRP) expression. FMRP functions as a translational regulator, affecting synthesis of many proteins including those involved in synaptic pruning during development.¹ Meta-analysis estimates the frequencies of individuals with the full mutation FXS allele to be approximately 1 in 7000 males and 1 in 11,000 females.² FXS is severely debilitating in males. Females generally are less affected than males due to mosaicism resulting from X-chromosome inactivation which occurs randomly early in embryogenesis.³

FXS presents with a variable clinical phenotype. In affected individuals, the disease presents during childhood with delayed developmental milestones. Intellectual deficit can be of variable severity and may include problems with working and short-term memory, executive function, language, mathematics and visuospatial abilities. Behavioral anomalies can be mild (e.g. anxiety, mood instability) to severe (e.g. aggressive behavior, autism). Autistic-like behavior can include hand flapping, poor eye contact, hand biting, gaze avoidance, social phobia, social and communication deficits and tactile defensiveness. In females, intellectual and behavioral disorders are typically milder than in males and usually consist of shyness, social and other forms of anxiety, and variable learning problems, with IQ ranging from normal to intellectually impaired. About 25% of girls have an IQ less than 70. Attention deficit hyperactivity disorder (ADHD) is present in over 89% of males and 30% of females and behavioral disinhibition is very common. Recurrent otitis media (50%) and seizures (12%) can also be observed. Individuals with FXS display a range of neuropsychiatric symptoms including intellectual disability, delayed language acquisition, poor social interaction, features of autism spectrum disorder, anxiety, hyperarousal, hypersensitivity, repetitive behaviors, disrupted sleep, attention deficit hyperactivity disorder and irritability/aggression.³ These behavioral changes are modelled in adult male *Fmr1* knockout (KO) mice which display a spectrum of behavioral phenotypes due to the *Fmr1* gene deletion. The mutant mice show hyperarousal in the open field test, have impaired social interaction, are less likely to build nests when provided cotton batting and are less likely to bury marbles in the cage bedding. Adult male mice have been used for most studies with animal models, as male FXS patients typically suffer more severe symptoms than do female patients due to the single X chromosome. In both humans with FXS `and the Fmr1 KO mice, there are alterations in the density, size, shape and maturity of dendritic spines, the principle recipients of excitatory inputs from other neurons.¹

Efforts to treat FXS have included numerous investigations have not been widely successful, which has led to revision of trial designs and exploration for additional and new therapies.³ Management of FXS is currently symptom-based and requires a multidisciplinary approach. Speech, physical and sensory integration therapy as well as individualized educational plans and behavioral interventions may be combined with medication, such as stimulants for attention deficit-hyperactivity disorder; selective serotonin reuptake inhibitors (SSRIs) for anxiety, depression, obsessive-compulsive

disorder; and atypical antipsychotic agents for self-injury and aggressive behaviors. New targeted treatments for FXS are being studied. Despite this slow progress, treatment of FXS remains still an unmet medical need.

